**Not applicable**

All questionnaires will be administered by the experimenter in a private room at the CRC. The experimenter will explain any instructions for each questionnaire and will be available to answer any questions a subject may have. The questionnaires at screening will take approximately 1 hour to complete. The questionnaires on each study day will take about 15 minutes to complete. See attached forms.

**Statistical Considerations:** Delineate the precise outcomes to be measured and analyzed. Describe how these results will be measured and statistically analyzed. Delineate methods used to estimate the required number of subjects. Describe power calculations if the study involves comparisons. Perform this analysis on each of the primary and secondary objectives, if possible.

### Statistical Analysis

**Analyses for Working Memory Performance Hypothesis Testing (H1a and H2a):** Comparisons of **MECA to placebo** will be conducted in support of **Hypothesis 1a**, while similar analyses comparing **NIC to placebo** will be used to test the hypotheses associated with **Hypothesis 2a**. The overall statistical model is:  $Y_{ijk} = \mu + s_{ik} + \pi_j + \tau_{t[i,j]} + \lambda_{d[i,j-1]} + x_k + \varepsilon_{ijk}$ , where  $Y_{ijk}$  is the value of the outcome of interest (**derived from the performance data described here and imaging data described below**) in subject k in sequence i at period j,  $\mu$  is the overall mean of the outcome of interest;  $s_{ik}$  is the effect of subject k in sequence i,  $i=1, 6$ ;  $\pi_j$  is the effect of period j,  $j=1, 3$ ;  $\tau_{t[i,j]}$  is the effect of treatment t,  $t=1, 2$  in period j of sequence i;  $\lambda_{d[i,j-1]}$  is the carryover effect of the treatment administered in period  $j_1$  of sequence i, where  $\lambda_{d[i,0]}=0$ ;  $x_k$  is the effect of baseline covariates for subject k; and  $\varepsilon_{ijk}$  is the random error (Jones and Kenward 2015). Because of the possibility of missing values in some of the measurements, we will employ a mixed effects model for these analyses, relying on the SAS proc mixed procedure for these analyses (Brown and Prescott, 2006).

**For this model, the effects of  $s_{ik}$  (subject) and  $\varepsilon_{ijk}$  (error) are considered random; all other effects are fixed.**

We will directly examine the effects of the drugs in older adults compared to younger adults. The mixed effects model will be adapted by the inclusion of additional variables to account for the effect of age group ( $g_{il}$  the effect of subject i in age group l; l=younger, older) and the treatment-by-age group interaction ( $g_{il} * \tau_{t[i,j]}$ ). The effect of interest in these analyses will be the interaction, which will test whether the effects of MECA or NIC differ with respect to the age of the subject. We predict there will be a significant interaction and will examine the age differences in response to the challenge drugs. For **performance analyses,  $p<0.05$**  will be used for statistical significance. We have used similar models in our prior work ([name] et al. 2012; [name] et al. 2009).

**Analyses for fMRI Hypothesis Testing (H1b and H2b):** Preprocessing and analysis of the functional data will be performed with Brain Voyager QX software (Brain Innovation, Maastricht, The Netherlands). The volumes will be realigned to the first volume to minimize the effects of head movements. Further data preprocessing comprises spatial (6 mm full-width half-maximum isotropic Gaussian kernel) as well as

temporal (high pass filter: 2 cycles/run) smoothing to remove aliased signal correlated with background respiration and heart rate. Anatomical and functional images are co-registered and normalized to Talairach space. Statistical analysis will be performed by multiple linear regression of the signal time course at each voxel. The expected BOLD signal change for each different type will be modeled by a canonical hemodynamic response function. One mean image per individual for the task-based contrast of interest (e.g. 3-back > 0-back) will be created. These contrast images will then be used for second level multi-subject/between group analyses using the standard ANOVA procedures described above.

The critical significance level for the **fMRI** will be  $p_{corr} < 0.001$ . To begin with, **whole brain analyses** will be used *because our hypotheses are about changes in activation in the working memory network and restricting the analysis to a region of interest may miss important effects of the nAChR drugs on brain activation.*

**Additional Analysis:** We will examine the **correlation** between working memory performance and MFG activation by conducting a regression analysis based on the difference between the placebo and nAChR blockade or stimulation conditions. First, we will compute difference scores for the performance measures and the percent signal change for the MECA and NIC study days compared to the placebo day. The differences scores for activation will then be used as the dependent measures in the analyses, while the difference scores for performance measures will serve as independent variables.

**Sample Size Calculations:** The sample size calculations are based on pilot data collected in our laboratory in separate studies: 1) older women with MECA and placebo challenges 2) younger adults during NIC and placebo challenges, and 3) older and younger adults with no challenge. We assume that, while the **fMRI** changes in younger adults will be in the same direction as older adults, the magnitude of the changes will be smaller. fMRI performed in younger adults during a 3-back condition showed a mean beta value of -1.12 in the **MFG**, compared to a mean of -0.54 in older adults. We assume that the MECA challenge in the younger adults will increase activation to a mean beta value mimicking that of the older adults on placebo (-0.54), while older adults will have an even greater activation increase to a mean beta of 1.00. Assuming a standard deviation of 0.40, a correlation of 0.35, both calculated from our pilot data, and a Type I error rate of 0.001, 13 subjects will provide 90% power to detect differences between younger and older adults in this region after MECA compared to placebo. A sample size of 19 younger adults and seven older adults will provide greater than 90% power to detect the within-group differences as statistically significant.

For **working memory performance**, sample size calculations are based on a Type I error rate of 0.05. The mean proportion correct for the 3-back performance in older adults was 0.75 compared to a mean of 0.88 in the younger adults, with a standard deviation of 0.13. We predict that the effect of the **MECA** challenge will be to reduce this accuracy measure in both the younger and older adults, with the older adults proportion correct decreasing to 0.60 while the decrease in younger adults will be less severe, decreasing to 0.83. Assuming a correlation of 0.35 a total of **48 subjects** will provide 90% power to detect differences on this test with MECA compared to placebo. This sample size will be sufficient to provide 90% power to detect a statistically significant decrease in performance among the older adults.

Consistent with our results of younger adults following **NIC** challenge, we assume that the effects of this stimulation will be in the opposite direction but similar in magnitude to those outlined above. We assume approximately a 20% drop-out rate; therefore, we will recruit 56 subjects/group, with the goal of **48 subjects/age group** completing the study.

For the correlational analyses, 48 subjects in each group will provide 90% power to detect a correlation of 0.46 as statistically significant and 80% power if the statistically significant correlation coefficient is 0.41.

**Risks/Benefits:** *Describe any potential or known risks. This includes physical, psychological, social, legal or other risks. Estimate the probability that given risk may occur, its severity and potential reversibility. If the study involves a placebo or washout period, the risks related to these must be addressed in both the protocol and consent. Describe the planned procedures for protecting against or minimizing potential risks and assess their likely effectiveness. Where appropriate, discuss plans for ensuring necessary medical or professional intervention in the event of adverse effects to the subjects. Discuss the potential benefits of the research to the subjects and others. Discuss why the risks to the subjects are reasonable in relation to the anticipated benefits to subjects and others. Discuss the importance of the knowledge gained or to be gained as a result of*

*the proposed research and why the risks are reasonable in relation to the knowledge that reasonably may result. If there are no benefits state so.*

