**Working Memory Task during fMRI:** Participants will complete a visual verbal **N-back Test** of working memory during the fMRI. This N-back task has three equivalent versions so that a different version will be administered on each study day. The specific version of the task will be counterbalanced across study days for each participant. These versions have been pilot tested with younger and older adults to ensure comparability of different versions and to ensure there is neither ceiling nor floor effects for performance for any age group.

*In this N-back task participants see a string of consonants (except L, W, and Y), presented in upper case letters, one every three seconds. Four conditions are presented: 0-back, 1-back, 2-back, and 3-back. The 0-back control condition had a minimal working memory load; participants are asked to decide if the current letter matches a single target letter that was specified before the epoch begins. In the 1-, 2-, and 3-back conditions, participants indicate whether the current letter on the screen matches a letter that is either 1, 2 or 3 back.*

*The 0-, 1-, 2-, and 3-back conditions are repeated three times in a counterbalanced order such that the same condition is not repeated two times in a row. In this block design task, participants respond to nine items in each block that takes 27 seconds. A rest break follows with a plus sign (+) fixation for 12*

seconds. The total time of the task is 8 minutes 12 seconds. Participants will practice the N-back task before drug dosing on each study day to ensure that they understood task instructions.

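### The age-comparison model lets drug effects, but not period effects, differ by age; adding age group-by-period is a nearly free safeguard with a small gain

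*Combined protocol and SAP*

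**What the plan says.** Statistical Analysis, under the performance hypotheses H1a and H2a, sets out a three-period, six-sequence crossover model with subject, period, treatment, carryover and baseline covariates. The period term "is the effect of period j". It carries no age index. Subject and error are random, and "all other effects are fixed".

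To compare the ages, the model gains "additional variables to account for the effect of age group" "and the treatment-by-age group interaction". No other term is added, and no section fits the model separately by age. The plan then names its target: "The effect of interest in these analyses will be the interaction".

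Three other places bear on the point:
- Working Memory Task during fMRI: "Participants will practice the N-back task before drug dosing on each study day". Three equivalent versions are counterbalanced over days. They were piloted in both ages to avoid ceiling and floor effects.
- Drug Challenge Procedures: drug order is random and balanced across the two age groups. No block size is given, and equal counts of the six sequences within each age are not stated.
- Sample Size Calculations: with about 20% dropout expected, "we will recruit 56 subjects/group", aiming for 48 completers per age group.

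**The concern.** Each participant meets the same type of task on three days, with a practice run and a scanned run each day, so accuracy may change from day to day. A common period effect allows for that change only if it is the same in both ages. The documents give no evidence that it is. The planning means on placebo (0.88 in younger adults, 0.75 in older) at least make different room for improvement possible.

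The test of interest is an age interaction. Letting the treatment effect differ by age while holding the main nuisance factor of a crossover common to both ages is an asymmetry that the plan does not justify. Two things could follow:
1. An age difference in learning inflates the residual and widens the interval for treatment-by-age.
2. If the six sequences are unequally represented in the analysed data, part of that difference can enter the treatment-by-age estimate.

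**Working it through.** **Inputs from Sample Size Calculations.** SD 0.13; within-subject correlation 0.35; 3-back means falling from 0.75 to 0.60 (older) and from 0.88 to 0.83 (younger) on mecamylamine; Type I error 0.05, taken as two-sided. The planned interaction is 0.15 − 0.05 = 0.10.

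**The plan's own figure.**
- SD of a within-subject difference: 0.13 × √(2 × 0.65) = 0.1482.
- Number per group for 90% power: 2 × (1.960 + 1.282)² × 0.1482² / 0.10² = 46.2, so 47.
- With 48 per age group, power is 0.911 (0.905 by the t version).

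The stated 48 therefore reproduces as 48 per age group.

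**Baseline precision.** Within-subject error variance is 0.13² × 0.65 = 0.010985. With 8 subjects per sequence per age, the SE of treatment-by-age is √(4 × 0.010985 / 48) = 0.0303. Power in the full three-day model is 0.908. Adding age-by-period leaves this SE unchanged and takes error degrees of freedom from 184 to 182.

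**Assumption.** The age difference in learning, d per day, is linear over days. The documents give no value; 0.02 to 0.05 per day is used, that is 0.04 to 0.10 from day 1 to day 3.

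**Effect on the residual, equal sequences.** A common period effect leaves each age off by ±d/2 per day. Per subject this adds 2 × (d/2)² = d²/2 to the within-subject sum of squares. Spread over two within-subject degrees of freedom it is d²/4.

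| d per day | added variance, d²/4 | relative to 0.010985 |
|---|---|---|
| 0.02 | 0.000100 | 0.9% |
| 0.05 | 0.000625 | 5.7% |

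Fitting the full model at 0.05 per day gives 96 × 0.00125 / 184 = 0.000652, or 5.9%. The SE then goes from 0.0303 to 0.0311, about 3% wider.

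**Effect on power.** Treating the wider SE as the true one takes power from 0.908 to 0.892 at 0.05 per day, a fall of 1.6 points. That is an upper figure. With equal sequences the learning difference enlarges the reported SE but does not make the estimate itself more variable. Allowing for this, power is Φ((0.100 − 1.97 × 0.0311) / 0.0303) = Φ(1.28) = 0.90, a fall of about one point. Simulation with 56 recruited and 56 × 0.8 ≈ 45 random completers per age agrees: SE 0.0322 without the term and 0.0313 with it, power about 88.0% against 88.9%. With equal learning the SE is 0.0313 either way.

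**Effect on the estimate.**
- Equal sequences: the shift is exactly zero.
- Random loss from 56 to 48 per age: the average shift is about zero. In 95% of trials it lies within 0.003 (day 1 to 3 difference 0.05) or 0.006 (difference 0.10). Partial dropout in a random-subject model gives the same limits.
- Simple randomisation without balance: within 0.008 or 0.014 for the same two differences.
- Systematic imbalance, with mecamylamine on day 1/2/3 in 22/16/10 subjects in both ages: −0.0094 or −0.0188. Mirrored imbalance in the two ages cancels; the same imbalance in both does not.
- With age-by-period fitted, the shift is zero in every layout tried.

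**The case against.** The strongest reply is that the harm is assumed. No section reports any learning effect, let alone one that differs by age. A difference of 0.05 per day means a gap of 0.10 by day 3, as large as the whole planned drug-by-age effect. Versions are counterbalanced and were piloted against ceiling and floor effects, and the pre-dose practice may itself reduce learning during the scanned run. An additive period effect is a common crossover specification, and carryover-by-age is absent too.

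Much of this stands. The size is hypothetical, and the piloting weakens any argument from ceiling effects. But counterbalancing removes version effects, not day effects, and freedom from ceiling and floor does not imply equal gains. Carryover is a weaker case: it needs a drug effect that lasts to the next visit, at least 48 hours later, whereas repeated testing occurs whatever the drug.

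Three stronger readings might be inferred, and the documents support none of them:
- *That dropout biases the age-by-drug estimate.* Random loss gives no average shift. A simulation shows one of about 0.003 to 0.004 only if the two subjects left over from 56 = 6 × 9 + 2 always go to the same two sequences. Drug Challenge Procedures specifies random order balanced across the ages.
- *That power suffers materially.* The loss is about one point in the least favourable case assumed.
- *That the imaging tests are compromised.* The planned imaging interaction is 1.54 − 0.58 = 0.96 with SD 0.40, and the plan claims 90% power at 0.001 with 13 subjects. No gain from the term was shown there.

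**Conclusion.** The gap is real and small. The model omits age-by-period while testing treatment-by-age, and neither the balanced sequences nor the counterbalanced versions remove an age difference in change over days. The cost of the omission is slightly lost precision and exposure to whatever sequence imbalance the one completed trial happens to have. That chance shift of up to about 0.006 is about one fifth of the SE. Shifts of 0.009 to 0.019 need sequence counts as unequal as 22/16/10 in both ages, which the plan neither intends nor, as written, rules out in the analysed data.

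These sizes rest on the plan's SD and correlation, on a linear learning difference of at most 0.05 per day, and on dropout unrelated to sequence. If the ages learn equally, the omission costs nothing and so does the remedy.

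**What to change.** In Statistical Analysis, add a fixed age group-by-period interaction to the age-extended model whenever treatment-by-age is tested on performance (H1a and H2a). Specify it before unblinding, so that there is no later choice between two models.

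The cost is one sentence and 2 of about 180 error degrees of freedom. Sample size, design and conduct do not change: with the term, 48 per age group still gives power of 0.908 for the planned interaction. It would also help to state that the six sequences are balanced within each age group. Using the same term in the second-level imaging model is optional, for consistency only.

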## METHODS AND PROCEDURES

**Study Design:** Describe the research design, including a description of any new methodology and its advantage over existing methodologies.

**Design:** Older adults (aged 65-75 years) and younger adults (aged 21-30 years) will participate in a screening visit and then three (3) nicotinic challenge study days which include performing a working memory task during fMRI. The nicotinic challenges will consist of 1) 20 mg oral mecamylamine, 2) 7 mg transdermal nicotine, and 3) matching placebos. After an extensive medical, behavioral, and cognitive screening we will enroll and complete 48 older adults and 48 younger adults.

**Procedures:** Describe all procedures (sequentially) to which human participants will be subjected. Identify all procedures that are considered experimental and/or procedures performed exclusively for research purposes. Describe the types, frequency and duration of tests, study visits, interviews, questionnaires, etc. Include required screening procedures performed before enrollment and while on study. Please provide in table, list or outline format for ease of review. (describe and attach all instruments)

Note: A clinical research protocol may involve interventions that are strictly experimental or it may involve some aspect of research (e.g., randomization among standard treatments for collection and analysis of routine clinical data for research purposes). It is important for this section to distinguish between interventions that are experimental and/or carried out for research purposes versus those procedures that are considered standard therapy. In addition, routine procedures performed solely for research purposes (e.g., additional diagnostic/follow-up tests) should be identified.

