**Medical Screening:** Participants will be physically healthy **nonsmokers** with a BMI  $\leq 32 \text{ kg/m}^2$ , and no cardiovascular disease other than mild hypertension. Participants will be assessed by history, physical exam, and laboratory tests assessing cardiac, hematopoietic, renal, hepatic, and hormonal function (CBC, CMP, TSH, U/A, ECG), and will have a medical history review and physical examination to establish general physical health. Blood will also be obtained for an **exploratory genetic analysis** to examine APOE and COMT genotypes as these genes have been shown to be important in cognition in older adults. APOE is important for cognitive decline in older adults and associated with cholinergic function (Espeseth et al, 2006). The COMT ValMet polymorphism modulates working memory performance in psychiatric populations (e.g. Meyer-Lindenberg & Weinberger 2006) but not in healthy subjects (Blanchard et al. 2011). However, it affects working memory-related brain activation (Jacobs & D'Esposito 2011).

Depending on the distribution of genotypes we will use this information as a covariate in the imaging analysis described below.

Once a participant passes the screening, s/he will be scheduled for **3 challenge and fMRI study days**.

**Pharmacological Challenges:** These procedures used for the nAChR challenges are similar to the procedures used in our prior studies ([name] et al. 2008; 2010; 2012; Carstens et al. 2011; [name] et al. 2009; 2012). The nAChR antagonist mecamylamine (**MECA**) will be administered at a dose of 20 mg orally as the hydrochloride salt. Placebos will consist of identical capsules filled with lactose. This dose of MECA is the same dose used in our prior studies in older women ([name] et al. 2008; 2012). Nicotine (**NIC**) will be administered with a 7 mg patch placed on the back of the shoulder for 45 minutes. Matching placebo patches will be used. This dosing procedure has utilized at UVM for many years to study the acute effects of nicotine in nonsmokers (Carstens et al. 2011; [name] et al. 2009; 2012). One dose of MECA, NIC, and placebo will require three challenge days for each participant.

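### Does indexing treatment as t = 1, 2, with a carryover term shared by both age groups, undermine the age-by-drug test?

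*Combined protocol and SAP*

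**What the plan says.** Under Statistical Analysis (H1a and H2a), the combined protocol and SAP introduces its equation with the words "The overall statistical model is". Sequences are indexed 1 to 6 and periods 1 to 3. For treatment the text reads "is the effect of treatment t, $t=1, 2$ in period j of sequence i". The carryover term "is the carryover effect of the treatment administered in period" preceding the current one, and it is zero in the first period. The levels of its index are not listed.

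The section begins with MECA against placebo for Hypothesis 1a, "while similar analyses comparing NIC to placebo will be used to test the hypotheses associated with" Hypothesis 2a. On age it says: "The mixed effects model will be adapted by the inclusion of additional variables to account for the effect of age group", together with the treatment-by-age interaction. No carryover-by-age term is added. It continues: "The effect of interest in these analyses will be the interaction, which will test whether the effects of MECA or NIC differ" by age.

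The design is a three-treatment crossover. Study Design states: "The nicotinic challenges will consist of 1) 20 mg oral mecamylamine, 2) 7 mg transdermal nicotine, and 3) matching placebos". Pharmacological Challenges states: "One dose of MECA, NIC, and placebo will require three challenge days for each participant".

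**The concern.** Two things look wrong.

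First, two treatment levels do not fit three treatments. One model with two drug-placebo contrasts is one reading. Two separate fits, each leaving out one drug day, is another, and the phrase about similar analyses for NIC gives it some support. In a MECA-placebo fit the preceding day may have been a NIC day, which then has a carryover effect but no treatment effect. Once carryover is in the model the two readings give different standard errors within an age group, so two analysts could report different results for the drug effect in younger or older adults.

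Second, the plan includes a carryover term but shares it across ages, while the effect of interest is a difference between ages. If carryover differed by age, that term would not remove the resulting bias from the interaction.

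**Working it through.** **Inputs.** Sample Size Calculations gives 3-back proportion correct on placebo of 0.75 (older) and 0.88 (younger), falling on MECA to 0.60 and 0.83; SD 0.13; correlation 0.35; Type I error 0.05; 48 completers per age group. Assumed: two-sided testing, complete data, and equal use of the six sequences (48/6 = 8 per sequence per age group).

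**The plan's own figure.**
- Interaction = (0.75 − 0.60) − (0.88 − 0.83) = 0.15 − 0.05 = 0.10.
- SD of a within-subject change = 0.13 × √(2 × (1 − 0.35)) = 0.1482.
- n per group for 90% power = 2 × (0.1482 × (1.960 + 1.282)/0.10)² = 46.2, so 47.
- At 48 per group, SE = 0.1482 × √(2/48) = 0.0303 and power = Φ(0.10/0.0303 − 1.960) = 91% (90.5% with the t distribution).

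The stated 48 therefore reproduces as 48 per age group. The calculation does not use the treatment index.

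**Which reading the layout supports.** Three treatments have 3! = 6 orders, each taking three periods. The equation has exactly six sequences and three periods, whereas two treatments given once each would need two of each.

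**Effect of the reading.** Generalised least squares with a random subject effect, period, treatment, age and treatment-by-age, and carryover shared by both ages:

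| Fit | Carryover parameters | Interaction SE (power for 0.10) | Younger-adult MECA-placebo SE (power for 0.05) |
|---|---|---|---|
| Joint or two-treatment | none | 0.0303 (91%) | 0.0214 (65%) |
| Joint | MECA and NIC | 0.0303 (91%) | 0.0226 (60%) |
| Joint | MECA only | 0.0303 (91%) | 0.0223 (61%) |
| Two-treatment | MECA and NIC | 0.0303 (91%) | 0.0254 (50%) |
| Two-treatment | MECA only | 0.0303 (91%) | 0.0234 (57%) |

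The within-age variance ratio, two-treatment to joint, is (0.0254/0.0226)² = 1.26 with two carryover parameters and about 1.11 with one. The older group has the same standard errors. Even at the largest, its assumed decline gives 0.15/0.0254 = 5.9 and power above 99.9%. Only the younger-adult decline of 0.05 loses material power, and the accuracy calculation claims none for it.

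**Effect of carryover that differs by age.** Label the orders MPN, MNP, PMN, NMP, PNM, NPM. Placebo directly follows MECA in two of the six (MPN, NMP), and MECA never follows itself. A MECA carryover of size λ in older adults only therefore shifts their average placebo day by λ/3 and biases the interaction by −λ/3. Both age groups use the same sequences equally, so a shared carryover term cancels from the age difference. It changes neither this bias nor the SE.

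The documents give no value for λ. As an assumed illustration, take 10% to 25% of the older adults' 0.15 decline, that is 0.015 to 0.0375:
- The interaction becomes 0.10 − 0.015/3 = 0.095, down to 0.10 − 0.0375/3 = 0.0875.
- Power becomes 88%, down to 82%.

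**What the design says about λ.** Drug Challenge Procedures requires at least 48 hours between study days and states that drug effects are gone by 1400 on the day of dosing. Potential Risks puts the end of mecamylamine's cognitive and physiological effects at 4 to 6 hours, which leaves about 48 − 6 = 42 hours before the next permitted day. Drug order is balanced across the age groups.

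**Cost of a carryover-by-age model.** Crossing the MECA and NIC carryover parameters with age gives SE 0.0324 and 87% power, but 0.24 of any age difference in placebo-day carryover still enters the MECA interaction. Removing that needs period, or placebo carryover, to be age-specific as well: SE 0.0335 and 85% power.

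**The case for a change.** The strongest case for a change is that the text conflicts with itself and a one-line correction would be cheap. Nothing in the section says outright whether there is one fit or two, or which carryover levels are used, and the same equation also serves the imaging outcomes. Hypothesis 1a includes impairment against placebo as well as the age difference, so a within-age variance ratio of 1.26 bears on something the study will report. Having judged carryover worth modelling, the plan uses a term that leaves its effect of interest untouched.

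The mismatch stands, and so does the algebra on the shared term. The inference that the test is therefore at risk does not. Under balance the interaction is the same under every reading, and the within-age effect with a stated power claim, the older adults' decline, stays above 99.9%. The carryover sizes needed to move the interaction noticeably are assumed and sit poorly with the stated washout. If lingering MECA impairment were greater in older adults, it would shrink the predicted interaction, not create it. Carryover in the opposite direction would inflate the interaction, again by only one third of the age difference.

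Two limits deserve mention. The 4-to-6-hour figure is for mecamylamine; for nicotine the documents offer only the statement about 1400. The exact cancellation needs equal sequence use and complete data, and the plan expects about 20% dropout, so in practice it will be approximate.

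**Conclusion.** No change follows. The treatment index is a clerical slip that the rest of the equation lets an analyst resolve: three treatments, one mixed model on all three days, and MECA-placebo and NIC-placebo as contrasts. Tidying the notation would alter no stated figure. The interaction keeps SE 0.0303 and about 91% power, and the 48 per group stands.

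Leaving out carryover-by-age is a fair trade-off. Such an analysis guards against an effect that the protocol's washout makes unlikely. If done without bias from any of the three preceding treatments, it lowers interaction power from 91% to about 85%. Reasonable statisticians differ on whether to run it as a sensitivity analysis.

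The conclusion rests on the plan's SD of 0.13 and correlation of 0.35, two-sided testing at 0.05, near-equal use of the six sequences in both age groups, mostly complete data, and the protocol's own statements about how long the drug effects last.

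### One residual variance for both ages probably makes within-age drug tests slightly liberal in older adults (about 6.6% at nominal 5%) and conservative in younger adults (about 3.5%); the interaction test keeps its size.

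*Combined protocol and SAP*

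**What the plan says.** The Statistical Analysis section (H1a and H2a) sets out a crossover mixed model with subject, period, treatment, carryover and baseline-covariate effects, to be fitted in SAS proc mixed. On the random part it says only that subject and error qualify: "error) are considered random; all other effects are fixed". Age is then added as a group effect and a treatment-by-age interaction, and the interaction is named as the effect of interest. No age-specific variance and no robust standard error is mentioned.

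Under Working Memory Task during fMRI, "participants respond to nine items in each block that takes 27 seconds", and each load is repeated three times.

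Under Sample Size Calculations, the 3-back placebo means are "0.75 compared to a mean of 0.88 in the younger adults, with a standard deviation of 0.13". On mecamylamine the plan expects "older adults proportion correct decreasing to 0.60 while the decrease in younger adults will be less severe, decreasing to 0.83". A single correlation of 0.35 is used. Besides the older-versus-younger comparison, the plan powers a within-age test: "This sample size will be sufficient to provide 90% power to detect a statistically significant decrease in performance among the older adults". Hypotheses 1a and 2a likewise state a drug-versus-placebo effect as well as an age difference in it.

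**The concern.** A proportion near 0.75 has more sampling variance than one near 0.88. If a single residual variance is estimated across both ages, the standard error of a drug contrast within older adults is too small and the one within younger adults is too large. The older contrast would then reject too often under the null and the younger one too rarely. At stake are the within-age drug-versus-placebo statements that go with H1a and H2a, mainly where effects turn out smaller than planned, and the power of the younger-adult comparison.

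**Working it through.** **Inputs from the documents.** Type I error 0.05 for performance (taken as two-sided; sidedness is not stated). Placebo means 0.75 older, 0.88 younger; mecamylamine means 0.60 and 0.83. One SD, 0.13; one correlation, 0.35. Responses per load per day: 9 x 3 = 27. Completers: 48 per age group.

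**The plan's own figure.** SD of a drug-placebo change = 0.13 x sqrt(2 x 0.65) = 0.1482. Interaction = 0.15 - 0.05 = 0.10. n per group = 2 x (1.960 + 1.282)^2 x 0.1482^2 / 0.10^2 = 46.2, so 47; by noncentral t, power is 0.899 at 47 and 0.905 at 48. The stated 48 therefore reproduces as a per-age-group figure. (As a total, 24 per group, power would be 0.63.) The implied residual variance is 0.0169 x 0.65 = 0.010985.

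**Sampling variance by age**, p(1-p)/27, assuming independent responses and all 27 scored:
- older, placebo: 0.75 x 0.25 / 27 = 0.00694
- younger, placebo: 0.88 x 0.12 / 27 = 0.00391

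The ratio is 1.78. Taking the between-subject variance (0.35 x 0.0169 = 0.0059) out of p(1-p) first gives 0.00673 and 0.00369, a ratio of 1.82.

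**Size of a within-age test that uses the pooled residual.** With 48 per group the pooled residual is the mean of the two ages. Actual size = 2 x [1 - Phi(1.96 / r)], where r = sqrt(own variance / pooled variance).

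| Scenario | Residual, older / younger | r, older / younger | Size, older / younger |
|---|---|---|---|
| (a) Sampling variance only | 0.00694 / 0.00391 | 1.131 / 0.849 | 8.3% / 2.1% |
| (b) Equal extra variance 0.00556 in each age, average residual 0.010985 | 0.01250 / 0.00947 | 1.067 / 0.928 | 6.6% / 3.5% |
| (c) SD 0.13 and correlation 0.35 hold in each age | 0.010985 / 0.010985 | 1 / 1 | 5.0% / 5.0% |

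The extra variance in (b) is 0.010985 - (0.00694 + 0.00391)/2 = 0.00556. Averaging the sampling variances over placebo and mecamylamine instead of placebo alone gives 6.8% and 3.3%. In the full three-period, six-sequence model with carryover terms, (a) becomes 7.9% / 2.4% and (b) 6.4% / 3.7%.

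**Compatibility with the stated SD.** Adding the between-subject variance 0.0059 to the residuals in (b) gives total SDs of about 0.136 and 0.124, either side of 0.13. Scenario (a) has an average residual of 0.00543, which with SD 0.13 needs a correlation of 1 - 0.00543/0.0169 = 0.68, not 0.35. Scenario (c) needs non-sampling variance of 0.00404 in older and 0.00707 in younger adults, 75% more in the young.

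**Interaction.** Its size is 5.0% in (a), (b) and (c) with 48 per group. With, say, 40 older and 48 younger completers it is 5.3% under (b) and 5.6% under (a).

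**Older mecamylamine contrast.** SE = 0.1482 / sqrt(48) = 0.0214, so z = 0.15 / 0.0214 = 7.0. Raising the SE by 7-13% leaves z at 6.6-6.2.

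**Younger mecamylamine contrast under (b).** True SE = sqrt(2 x 0.00947/48) = 0.0199; pooled SE = sqrt(2 x 0.010985/48) = 0.0214. Power for the 0.05 drop is Phi[(0.05 - 1.96 x 0.0214)/0.0199] = 66% with the pooled SE and Phi[0.05/0.0199 - 1.96] = 71% with the age-specific one.

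**The case against.** The best reply is that the plan gives one SD and one correlation without splitting them by age. Both sampling variances fit under 0.010985, so its figures are compatible with equal residuals and a 5% size in each age. That stands, and it is why 5% belongs in the range. Its weakness is that it needs clearly more day-to-day variance in younger adults, for which the documents offer no support.

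The single residual is also inferred from silence. The plan does not state homogeneity across ages, nor whether within-age contrasts come from the joint model or from separate fits by age; separate fits would remove the problem. This stands too, and is a reason to specify the point.

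A reader might go further in three ways that the documents do not support:
- That the 27-response proportions by themselves imply 8.3% and 2.1%. This needs zero other day-to-day variance, against the plan's own correlation.
- That a significant mecamylamine decrement in older adults would rest on an understated standard error. At the planned effect, z stays above 6.
- That the main test is compromised. The interaction keeps its size with equal groups when variance differs only by age, and moves little with moderately unequal dropout.

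**Conclusion.** The point holds as a modest improvement to the within-age contrasts. Best estimate: about 6.6% in older and 3.5% in younger adults at nominal 5%. Plausible range: 5-8% and 2-5%. The estimate rests on equal non-sampling variance by age, an average residual at the plan's 0.010985, variance that does not depend on treatment, and contrasts taken from a joint fit with one residual.

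If variance also follows the treatment means the plan predicts, with nicotine equal and opposite to mecamylamine, age grouping alone is not enough: the calculated sizes spread to about 5-11% in older and 1.3-4.4% in younger adults, and the interaction contrasts also move off 5%. That arises from pooling over treatments and bears on the choice of remedy.

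**What to change.** In the Statistical Analysis section, let the residual and subject variances differ by age group (GROUP=age on the REPEATED and RANDOM statements in proc mixed) with Kenward-Roger degrees of freedom. Alternatively, specify robust standard errors, which also cover variance that changes with treatment. State that all within-age drug contrasts come from that fit.

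The cost is two extra variance parameters and a change to the planned SAS code, with no new data. Each within-age contrast would have roughly half of the joint model's 186 within-subject degrees of freedom, which moves the critical t only from about 1.97 to 1.99. If the variances prove equal, results will hardly change.
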